2.3 Specific Aims

2.3.1 Specific Aim 1

Primary Objective. The primary objective of the study is **to establish which immunosuppressive treatment, methotrexate or mycophenolate mofetil, results in a higher rate of corticosteroid-sparing treatment success, on an intent to treat basis.** Specifically, we will compare the fraction of subjects who achieve treatment success at six months (as defined in the Manual of Operations Section 2.5.1) between the two groups.

Primary Outcome. The primary outcome for Specific Aim 1 will be the difference in the proportion of patients assigned to mycophenolate mofetil vs. methotrexate who achieve treatment success (as defined in the Manual of Operations Section 2.5.1).

Patients who experience success at 6 months with the drug to which they were originally randomized (in Specific Aim 1) will continue on the same drug for an additional 6 months. This will be called Phase I (6-12 months). Patients will then be seen every 3 months (and will be examined at 9 months and at 12 months), until success at 12 months or treatment failure at any time. Patients who fail treatment before 12 months with the initial drug will be removed from the study and treated according to best medical judgment.

Secondary Objectives

- To determine whether patients exhibit a difference in time to control of inflammation within the first six months.
- To determine whether patients exhibit a difference in time to corticosteroid sparing control of inflammation within the first six months.
- To evaluate the proportion of patients achieving treatment success at 5 months and sustaining, for at least 28 days, to 6 months.
- To evaluate a difference in control of inflammation in the posterior/pan anatomic locations only, assessed at by six months.
- To evaluate a difference in control of inflammation in the interior and anterior/intermediate anatomic locations only, assessed at by six months.
- To determine whether there is a change in best spectacle-corrected visual acuity at six months.
- To determine whether patients treated exhibit a difference in health related quality of life at six months.
- To determine if there are differences in discontinuing treatment due to each of the following reasons: safety, intolerability or lack of efficacy at six months.
- To determine whether patients exhibit a difference in the proportion of patients having macular edema at 6 months
- To determine whether patients exhibit a difference in macular thickness at 6 months

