3.1 Baseline characteristics

At baseline, each eye (1) may be fully able to be assessed, (2) it may be possible assess part of the eye, but not be possible to assess the entire eye, or (3) it may not be possible to assess any of the eye. For each eye for which some assessment is possible, either (1) the eye shows no signs of uveitis, or the eye may show some signs of uveitis, but fail to meet the severity criteria (1+ anterior chamber cells, vitreous haze or no active retinal/choroidal lesions, as defined in the Manual of Operations), or (2) the eye meets the severity criteria as defined in the manual of operations. Some patients are monocular at baseline, one eye being either absent, or exhibiting such disease as to preclude the possibility of ever assessing the eye (i.e. phthisis).

For this trial, we summarize the above possibilities as follows. Each eye (OD or OS) may be classified into one of the following types at baseline:

- A. Eye fully assessible, does not meet the severity criteria as defined in the MOP
- B. Eye partially assessible, does not meet the severity uveitis criteria in the assessible region
- C. Eye fully assessible, meets severity criteria
- D. Eye partially assessible, meets severity criteria in assessible region
- E. Eye absent or too diseased to ever assess

Patients, not eyes, are the unit of assignment and of randomization. Thus, there are twenty-five possible types of patients. A patient is required to have at least one eye which meets severity criteria for uveitis, and which can be completely assessed. Eligibility is summarized in the following table; cells indicate the possibility of enrollment for a patient whose right eye classification corresponds to the row and whose left eye classification corresponds to the column (A-E being defined in the previous paragraph).

	OS: A	OS: B	OS: C	OS: D	OS: E
OD: A	Not eligible	Not eligible	Eligible	Not eligible	Not eligible
OD: B	Not eligible	Not eligible	Eligible	Not eligible	Not eligible
OD: C	Eligible	Eligible	Eligible	Eligible	Eligible
OD: D	Not eligible	Not eligible	Eligible	Not eligible	Not eligible
OD: E	Not eligible	Not eligible	Eligible	Not eligible	Not eligible

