Assessment and follow-up depends on the status of the eye. Eyes classified as type E above are recorded as such at baseline, and never provide eye outcome related data. Because (a) inability to assess parts of the eye could be related to the progression of disease, but (b) inability to assess in the absence of signs of disease cannot be considered evidence of treatment failure, we use the following table to summarize how success at six months will be scored. In this table, the row corresponds to the status of an eye at baseline, and the column to the status of the eye considering the primary outcome of success at six months.

	Month 6: A	Month 6: B	Month 6: C	Month 6: D	Month 6: E
Baseline: A	Success	See below**	Fail	Fail	Fail*
Baseline: B	Success	See below**	Fail	Fail	Fail*
Baseline: C	Success	See below**	Fail	Fail	Fail*
Baseline: D	Success	See below**	Fail	Fail	Fail*
Baseline: E	NA	NA	NA	NA	NA

Specifically, note that an eye which is fully assessable at six months and which does not meet the specific criteria for failure of control is always considered a success. Eyes which are fully or partially assessable and which meet any of the criteria for failure are always considered to have failed. However, eyes which are only partially assessable but which meet no criteria in the assessable region may be scored successes or failures depending on their baseline status (see next paragraphs below). Eyes which were present at baseline but which are missing at the end of the study are listed as Fail* in the table; we propose to consider such eyes to have failed unless a specific reason demonstrates that the loss of the eye was completely unrelated to the presence or progression of disease.

The primary analysis is at the patient level. Both eyes must meet the success criteria for the patient to be considered a success.

****Incompletely assessable eyes.** Uveitis assessment for this purpose is based on (i) assessment of anterior cells, (ii) vitreous haze, and (iii) retinal or choroidal lesions. In the pilot study, (iv) assessment of vitreous cells was also used. We will have longitudinal measurements of inflammation according to the following schedule: anterior chamber cells, vitreous haze and

active retinal/choroidal lesions will be measured at Baseline, Week 2, Month 1 and every subsequent 4 weeks until the 6 month assessment (Phase I or Phase II) or 9 and 12 month assessment (Phase I 6-12 months).

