Selected secondary outcomes, including vision, macular edema, time to control of inflammation, will be analyzed at the eye level. All eyes that meet inclusion criteria of inflammation at baseline will be included in this analysis. Linear or generalized linear mixed modeling will be conducted (see below for details).

The following is a brief summary of general guiding principles.

- For the primary outcome, if any portion of the eye cannot be assessed at baseline, and it *still cannot be assessed at Visit 6 or Visit 12*, if all other markers of success are met, this portion of the eye would be considered to have had successful therapy.
- For the primary outcome, if any portion of the cannot be assessed *by Visit 6 or 12* and this

same portion of the eye was *completely assessable* at baseline, if all other markers of success are met, then the last worst observation for this eye would be carried forward and used at the assessment of this eye portion.

- For the primary outcome, if an eye *becomes missing by Visit 6 or 12*, and it is related to uveitis (regardless of its disease status at baseline) if all other markers of success are met, this patient should be considered a failure.

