1. *Twelve-month endpoint for successes.* We propose to compare the proportion who maintain successful control for twelve months (i.e. the outcome is the proportion who have achieved control in all study eyes both at the six month visit and at the 12 month visit) between the two study arms. Per protocol, patients with successful control of their inflammation at 6 months remain on the same treatment until 12 months. We will use the same statistical model (and Wald procedure) as for the primary analysis. We test the hypothesis that the coefficients for treatment assignment and treatment assignment/anatomic location interaction both equal zero.

2. *Time to corticosteroid sparing control of inflammation.* We propose to use a Cox proportional hazard model with the outcome being the time to (1) first steroid-sparing control, and separately (2) first control of inflammation, with treatment assignment (and interaction) as the predictors. Time to first steroid-sparing control is the principal prespecified analysis here; alternative approaches will be conducted for additional insight and as sensitivity analyses. We will supplement this analysis with a parametric survival analysis using the Weibull distribution and also with a gamma distribution (note that individuals may drop out at any time, not just at the monthly visits), and with a method treating the time to success as interval censored. The outcome for this analysis is a single number for each patient (not for each eye). The primary statistical

result will be the Wald test for the treatment assignment coefficient. We will repeat the analysis using study site as a fixed effect in this model (and as a sensitivity analysis, will explore random-effects survival analytic methods which are becoming available, see Pankratz et al.).⁶ In supplementary analyses we will include age and anatomic location as additional covariates.

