7. *Successful control of inflammation with complete discontinuation of steroids (Phase I 6-12 months).* Some individuals may be able to taper completely off of steroids while maintaining control of inflammation. The outcome variable is the fraction of individuals achieving such control in both eyes (out of the number of individuals starting therapy). We propose to compare this fraction between the two treatment groups using logistic regression. The statistical analysis will otherwise be identical to the primary analysis.

8. *Macular edema.* We wish to compare the fraction of patients with macular edema at 6 months, between the two treatment arms. This will be conducted using the Fisher exact test, with a two-sided test at alpha of 0.05. Supplementary analyses will be based on logistic regression using the presence of macular edema as a binary outcome variable, with regressors ("independent variables") of treatment arm and anatomic location. Further analyses (including other baseline covariates or other subsets) will be labeled as exploratory.

9. *Change in Macular thickness.* We propose to test the hypothesis that macular thickness is different in the two treatment arms, at 6 months. We propose to model the macular thickness at 6 months using two regressors: treatment arm and baseline thickness. We will test the hypothesis that treatment arm is associated with final macular thickness, using the T-test of the regression coefficient for treatment arm in the model including baseline thickness as a second covariate (two sided using $\alpha=0.05$). We will examine residuals for normality and homoskedasticity, and prepare residual vs fitted value plots. Standard transformations will be used in case of evidence that the assumptions have been violated.

We will also look at change in macular thickness in only patients who had macular edema at Baseline.

10. *Bayesian analysis.* Prior to data collection, we will elicit a Bayesian prior for the effect size (difference between the two treatment arms) from a group of uveitis experts, using methods our group has previously applied to the [REDACTED]. The likelihood

function corresponding to Equation (1) will be used to yield a posterior distribution for the effect size. Quantiles of this distribution will be reported, together with sensitivity analyses (with respect to model choice, influential observations, and prior distribution).

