4. *Quality of life.* For a power calculation, we consider the SF-36 questionnaire, which has two scales, the MCS and the PCS. The raw score standard deviation will be assumed to be 8.4 points; we assume a correlation between baseline and six months of 0.6.^{16, 17} Assuming that the baseline score will “explain” roughly 36% of the variance allows us to assume a corrected raw score standard deviation of 6.72 in a simplified calculation in which we treat the analysis as a T-test. The same power calculation formula used in (3) above reveals that **our sample size provides approximately 80% power to detect a raw score difference of roughly 2.57 between the two treatment groups.** This difference is roughly comparable to the small difference in scores found between intermediate uveitis patients and the general population¹⁶, a difference we believe to be more than sufficient to detect clinically significant results. Note that the population mean of this score is standardized to 50 on 0 to 100 scale. Similar analyses will be conducted for the vision related quality of life (i.e. NEI-VFQ-25 and the IND-VFQ).

5. *Rate of discontinuation.* Based on retrospective studies, we expect approximately 13% to discontinue methotrexate due to tolerability and 5% to discontinue due to safety (laboratory abnormalities or other serious adverse events). We expect approximately 4% to discontinue mycophenolate mofetil due to tolerability and 5% to discontinue due to safety.^{12, 18-20} For the purpose of the power calculation, we assume 10% loss to follow-up and consider only the comparison of discontinuation due to tolerability. **We use the power formula given in Freedman et al (p. 104) to calculate a power of 61% for this comparison.**³

6. *Macular edema.* Previous studies suggest approximately 38% of individuals with uveitis will manifest macular edema.²¹ **We have approximately 80% power to detect a difference of a factor of two in the final proportion of macular edema (19% vs 38%).**

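### Macular edema has two conflicting analyses in the SAP (patients by Fisher test, eyes by mixed model), and the main test leaves out baseline edema that is already collected

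*Combined protocol and SAP*

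**What the plan says.** **Patient version.** SAP 3.2.2 item 8 compares the fraction of patients with edema at 6 months between arms: "This will be conducted using the Fisher exact test, with a two-sided test at alpha of 0.05". The supplementary logistic model has arm and anatomic location; other baseline covariates are exploratory. SAP 2.3.1 has the same unit: "To determine whether patients exhibit a difference in the proportion of patients having macular edema at 6 months". SAP 3.4.2 item 6 states about 80% power for 19% versus 38%, with the 38% taken from a proportion of individuals with uveitis.

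**Eye version.** SAP 3.1 says "Selected secondary outcomes, including vision, macular edema, time to control of inflammation, will be analyzed at the eye level", and then "All eyes that meet inclusion criteria of inflammation at baseline will be included in this analysis". It names linear or generalized linear mixed models as the method and points to details further on.

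**Two-eye rules.** For the primary outcome SAP 3.1 says "Both eyes must meet the success criteria for the patient to be considered a success". For anatomic site, SAP 3.1.3 uses the most serious involvement. Neither section mentions edema.

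**Baseline edema.** OCT is scheduled at baseline (protocol 4.2 and 4.3.3), and edema is judged from it (protocol 5.4.3). SAP 3.2.2 item 9 already selects a subset with edema at baseline. The regressor list in SAP 3.2.1 contains baseline acuity, haze and macular thickness, but not baseline edema.

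**The concern.** The details that SAP 3.1 points to turn out, in item 8, to have a different unit, a different method and no eye restriction. The sentence in 3.1 is not idle text: item 4 carries it out for visual acuity, with one outcome per eye, a patient random effect and the same eye restriction. An analyst could follow it for edema in good faith.

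Even if item 8 governs, it cannot be computed without deciding what makes a patient positive: either eye, both eyes, or the qualifying eye. The reading is open too, since protocol 5.4.3 has the site judge edema in real time and protocol 10.3 has the reading center assess edema type. Left open, these choices could be made after the data are seen.

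Leaving out baseline edema is a smaller matter. It may cost some power, and it leaves chance imbalance between arms uncorrected in the estimate.

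**Working it through.** **1. The plan's power figure.** Inputs: 38% versus 19% (SAP 3.4.2 item 6); 108 per arm with 10% loss (SAP 3.4.1), so 108 × 0.9 = 97.2, taken as 97; two-sided alpha 0.05. Power is the sum, over all pairs (a, b) that the test rejects, of Bin(a; 97, 0.38) × Bin(b; 97, 0.19). Size is the same sum with both rates at (38% + 19%)/2 = 28.5%.

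| Unadjusted test | Power | Size |
|---|---|---|
| Fisher exact | 80.5% | 3.5% |
| Fisher, mid-P | 83.8% | 4.8% |
| Likelihood ratio | 84.5% | 5.1% |

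The stated figure is reproduced. Leaving Fisher alone gives 84.5 − 80.5 = 4 points.

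**2. Do the two versions measure the same thing?** SAP 3.1 requires only this: "A patient is required to have at least one eye which meets severity criteria for uveitis, and which can be completely assessed". Its eligibility table admits a patient with one fully assessable eye that meets the severity criteria and one that does not. If the only 6-month edema is in the second eye, the patient is positive under item 8 read as either eye, but that eye is outside the set in 3.1. In the other direction, a patient with two qualifying eyes enters the eye analysis twice. SAP 2.3.1, 3.2.2 item 8 and 3.4.2 item 6 all count patients or individuals, so 3.1 is the outlier. It also puts time to control at the eye level, where 3.2.2 item 2 uses one value per patient.

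**3. Gain from baseline edema.** The documents give no baseline-to-month-6 association, so the odds ratio (OR) and the baseline prevalence (30%, 38%, 50%) are assumed. Logistic likelihood-ratio test on arm and baseline edema, 97 per arm, marginal rates held at 38% and 19%, 40,000 simulated trials per scenario (simulation error about 0.2 points, size 5.1–5.5%):

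| Assumed OR | Adjusted power at prevalence 30/38/50% | Gain over unadjusted likelihood ratio (points) |
|---|---|---|
| 1 | 84.4 / 84.7 / 84.3 | 0.0 / 0.0 / −0.1 |
| 2 | 85.6 / 85.0 / 85.7 | 0.9 / 0.9 / 0.9 |
| 3 | 86.2 / 86.4 / 86.7 | 1.9 / 2.1 / 2.0 |
| 6 | 89.4 / 89.5 / 89.0 | 4.9 / 5.2 / 4.6 |
| 12 | 93.2 / 93.0 / 91.5 | 8.7 / 8.5 / 7.3 |

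With a block-permutation P-value as in SAP 3.2.2 (assumed layout of nine sites with 75% of patients in two; 3,000 trials of 999 permutations; prevalence 38%), adjusted power is 84.7%, 85.3% and 92.0% at OR 1, 3 and 12, with size 5.0–5.2%.

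**4. Chance imbalance.** The standard deviation of the arm difference in baseline prevalence π is √(2π(1−π)/97). At π = 38% this is 7.0 points, and the arms differ by 10 points or more in 16% of randomizations (14–17% for π from 30% to 50%). Let d be the 6-month edema risk with baseline edema minus the risk without it. At π = 38%:

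| OR | d in the 38% arm | d in the 19% arm |
|---|---|---|
| 3 | 0.540 − 0.282 = 0.26 | 0.298 − 0.124 = 0.17 |
| 12 | 0.716 − 0.174 = 0.54 | 0.411 − 0.055 = 0.36 |

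A 10-point imbalance, 5 points in each arm, moves the unadjusted difference by 5 × (0.26 + 0.17) = 2.2 points at OR 3 and 5 × (0.54 + 0.36) = 4.5 points at OR 12. At OR 1 it moves it by 0. The planned difference is 19 points.

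**The case against.** The specific item can be said to govern over the general section, and an unadjusted main test with adjusted supplements is an ordinary choice in this SAP. The main acuity model (3.2.2 item 4) is a change score on treatment, with baseline acuity as a covariate only in a supplement, and the primary model has arm and site alone. Both statements about those models are right. So although quality of life, macular thickness and vitreous haze adjust for baseline in their main analyses, baseline adjustment is not a uniform rule that item 8 breaks. But no passage says that item 8 overrides 3.1, and such a rule would still not define a patient's edema status.

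The upper end of the power gain also lacks support. All patients start oral prednisone (protocol 3.2.1), and one injection for persistent edema is permitted in the first 90 days (protocol 3.2.4). Either could weaken the link between baseline and month 6. This stands, and the gain must be called unknown.

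Some baseline eyes may be ungradable, since SAP 3.1 expects partly assessable and absent eyes. Adjustment therefore needs a rule that keeps those patients; the simulations assume complete baseline data.

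Finally, the study forms and the reading center manual (Appendices A and E) are listed but not supplied. A two-eye rule may stand there, so its absence is established only for the supplied text.

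**Conclusion.** The point stands as an improvement worth making, not as an error in the test. The conflict between SAP 3.1 and 3.2.2 item 8 on unit, method and eye set is certain from the text. The missing two-eye rule is certain for the text supplied. Both justify a correction whatever the power gain.

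The covariate gain is about 0, 1, 2, 5 and 7–9 points at assumed odds ratios 1, 2, 3, 6 and 12. It rests wholly on those assumptions.

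Three stronger readings are not supported:

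- A reader might infer that the Fisher test or its 80% power is wrong. Both are sound; the test is only conservative.
- A reader might credit the whole rise from 80.5% to baseline edema. Four points of it come from leaving Fisher.
- A reader might take chance imbalance for a bias in the planned test. Randomization and the type I error already allow for it. The shifts in the working are the same loss of precision that the power figures count.

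**What to change.** 1. Correct SAP 3.1 so that macular edema is analyzed by patient, in agreement with 3.2.2 item 8, and bring time to control into line with 3.2.2 item 2.
2. Define patient-level edema from the two eyes identically at baseline and 6 months, for example edema in either eye. State how an absent or ungradable eye counts, and whether the site or the reading center reading is used.
3. Make the main test a logistic regression of 6-month edema on arm and baseline edema, with site as in the primary model. The block-permutation P-value can be reused. Report a standardized risk difference beside the odds ratio, so that item 8's comparison of fractions is kept.
4. Keep patients with ungradable baseline edema in the model through a missing-indicator category, so that none is dropped.
5. Add baseline edema to the regressor list in SAP 3.2.1, and keep Fisher as supplementary.

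The cost is SAP wording; baseline OCT is already collected. Closed reports tabulate outcomes by arm (SAP 6.2.2) and the principal statistician is unmasked for the interim analyses (SAP 3.10.2). The change should therefore be dated, justified, and documented as made without by-arm edema data.

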5.4. Optical coherence tomography

We will be using spectral-domain optical coherence tomography (SD-OCT) in this study to monitor the effects of treatment by measuring macular thickness and changes in macular thickness. We will be utilizing the Heidelberg Spectralis SD-OCT unit for all study assessments. Each site must have access to the Heidelberg Spectralis unit at the time of study initiation and must continue to use that same scanner for all patients for the duration of the study. If Heidelberg Spectralis is not available, the Zeiss Cirrus SD-OCT may be used.

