2.4 Randomization

2.4.1 Stratification between sites

Patients will be recruited from nine sites: [REDACTED]

[REDACTED] (see Manual of Operations Section 2.2 for details). Patients will be randomized to two treatments (arms): methotrexate (X) or mycophenolate mofetil (Y). The treatment protocols are specified in the FAST Uveitis Trial Manual of Operations.

Within each site, assignments will be conducted using a block randomization scheme with randomly varying block sizes.

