The primary analysis is a logistic regression with treatment arm as a predictor. For the primary analysis, we propose to use study site as a *random effect* (random intercept model). The null hypothesis is that the regression coefficient for treatment arm equals zero, which will be tested using a likelihood ratio test with one degree of freedom. We will also fit the following models: (a) a model including drug, site, and drug \times site interaction, (b) a model including only drug and site, (c) a model including only drug and country, and (d) a model with drug, country, drug-country interaction, and site within country. Countries or sites with fewer than three observations will be pooled together. Provided there is no evidence of treatment \times site interaction or treatment \times country interaction, we will report pooled treatment effects and confidence intervals. In the event evidence suggests a difference between treatment sites, we will report treatment effects by site, and repeat the analysis excluding particular sites. Similarly, evidence of a treatment \times country interaction will lead us to report treatment effects and confidence intervals by country.

Simulations suggest that use of a model containing interaction terms between site or country and treatment for the primary analysis is undesirable. Such a procedure results in modest loss of power unless the treatment effect is of opposite sign in different sites or countries.

The hypothesis test is to be two-sided with alpha of 0.05. We propose to compute the P-value by permutation testing, based on the block randomization scheme.

Prespecified Subgroup Analysis.

The prespecified subgroup analysis will test the hypothesis that there is a treatment effect separately in each anatomic group, using a logistic regression model.

We denote the two anatomic groups by X_i^3 , which equals 0 when the patient is in the intermediate group and 1 when the patient is in the posterior/pan group. In the intermediate subgroup, we plan to determine whether there is evidence of a treatment effect (regardless of the effect in the posterior/pan group). Specifically, we will conduct this analysis in two ways: anatomical site at enrollment (split into three categories: anterior, anterior/intermediate or intermediate only, and posterior/panuveitis), and anatomical location by history (split into two

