3. *Country and site within country.* We denote the country by X_i^2 , which will be 0 for US locations and 1 for Indian locations; X_n^4 is 1 only for patients in the second Indian site and 0 otherwise, while X_{iz}^4 is 1 only for patients in the second US site and 0 otherwise. As mentioned under the Primary analysis, we propose to fit models with country only, drug by country interaction, and with a drug by country interaction, including site within country as well. Analysis will be conducted within each site, then pooling the sites within country together. Further details regarding pooling across centers are provided above under the main prespecified analysis.

4. *Best spectacle-corrected visual acuity (BSCVA).* The primary outcome variable for this secondary outcome will be the change in best spectacle-corrected visual acuity from baseline to final (as defined in the FAST MOP, i.e. for those who successfully control inflammation as defined in the MOP, or at the time of failure for those who fail; MOP, Section 2.6). Visual acuity change scores are available for both eyes for each patient.

The primary analysis will use a linear mixed-effects regression, where the outcome variable is the change in BSCVA in each eye, using treatment assignment as a statistical predictor (regressor, independent variable); a random effect will be used at the individual level, because of the possibility that changes in the two eyes from a given patient are correlated. In a supplementary analysis, we will include as predictors (independent variables) anatomic location of uveitis, interaction between anatomic location and treatment assignment, and the study site, together with a random effects for patient. We will fit these models using maximum likelihood (R procedure `lmer`) and use likelihood-ratio tests to test the hypothesis that treatment assignment affects BSCVA change. Only eyes that are eligible and meet inflammation criteria at baseline will be included in this analysis. If at a given visit, vision cannot be assessed, we will carry the last observation forward. Additional sensitivity analyses for missing data will be used (including mixed effects models controlling for time, including all data from an individual).

Also, if there is no eye at Month 6 to assess, the patient will be given a logMAR value of 2.0.

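### Five lead secondary analyses omit study site, the factor randomisation was blocked on; if site is prognostic they are conservative and lose power

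*Combined protocol and SAP*

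**What the plan says.** SAP 2.4.1 states: "Patients will be recruited from nine sites". It adds: "Within each site, assignments will be conducted using a block randomization scheme with randomly varying block sizes". SAP 3.2.2 then fits the primary outcome by logistic regression with a site random intercept, takes the P-value from a permutation test that follows the blocking, and pools sites with fewer than three observations.

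The planned secondary analyses in SAP 3.2.2 differ among themselves:

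- **Site in the lead analysis:** items 1 and 7, which reuse the primary model; item 5 (quality of life, random effect); item 6 (reason for discontinuation, fixed effect in the polytomous model).
- **Site only in a second fit:** item 2 (time to control) leads with a Cox model "with treatment assignment (and interaction) as the predictors", and then says "We will repeat the analysis using study site as a fixed effect in this model". Item 4 (BSCVA) says "The primary analysis will use a linear mixed-effects regression, where the outcome variable is the change in BSCVA in each eye, using treatment assignment", with a patient random effect; site enters a supplementary model.
- **No site-adjusted version committed:** item 8 (macular edema, Fisher exact test; the supplementary logistic model has arm and anatomic location only), item 9 (thickness: "We propose to model the macular thickness at 6 months using two regressors: treatment arm and baseline thickness") and item 12 (vitreous haze; baseline haze, follow-up time and treatment).

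The general rule that opens the planned secondary analyses, on repeating models with and without site terms, covers only models that already contain a site effect. It therefore never adds site to items 8, 9 or 12.

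**The concern.** Blocking within site balances the arms on whatever differs between sites, so between-site variation does not contribute to the true sampling error of the treatment contrast. An analysis that ignores site still counts that variation as noise. If site predicts the outcome, the test rejects less often than its nominal level and power is lost. The SAP accepts this reasoning for the primary outcome and gives no reason for departing from it in these five. At stake is efficiency on several of the main secondary outcomes. There is also a reporting question: a site-adjusted edema result produced later would probably carry the exploratory label that item 8 gives to further covariate models.

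**Working it through.** **Inputs from the documents.** 108 per arm (Protocol 2.1, SAP 3.4.1); 10% loss by six months, so 108 × 0.9 ≈ 97 per arm; thickness SD 160 microns and target difference 65 (SAP 3.4.2, item 7); acuity-change SD 6.5 letters and target 2.63 (SAP 3.4.2, item 3); two-sided alpha 0.05; nine sites.

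**Assumed.** ρ, the share of residual variance lying between sites. The documents give no figure, so it is shown from 0 to 0.20.

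**The plan's own figures.** For thickness, SE = 160 × √(2/97) = 22.97; 65/22.97 = 2.83; power = Φ(2.83 − 1.96) = 0.808, or 0.804 with the t distribution. For acuity, SE = 6.5 × √(2/97) = 0.933; 2.63/0.933 = 2.82; power 0.805, or 0.801 with t. Both reproduce the stated 80% or so.

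**Linear models (items 4 and 9).** With site in the model the SE is multiplied by √(1 − ρ), and 8 degrees of freedom are used for nine sites. The half-width is the t quantile times the SE.

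| ρ | Thickness 95% half-width, no site | With site | Excess width | Thickness power with site | Acuity power with site |
|---|---|---|---|---|---|
| 0 | 45.3 | 45.3 | 0% | 0.804 | 0.800 |
| 0.05 | 45.3 | 44.2 | 2.6% | 0.823 | 0.820 |
| 0.10 | 45.3 | 43.0 | 5.4% | 0.843 | 0.840 |
| 0.20 | 45.3 | 40.5 | 11.8% | 0.882 | 0.880 |

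The percentages are ratios (for example 45.32/40.54 = 1.118) and do not depend on the SD of 160.

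**Simulation of the thickness comparison.** SAP block sizes (4 with probability 2/3, 6 with probability 1/3), 10% loss, assumed unequal sites, 3000 runs.

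| ρ | Reported SE, no site | Actual sampling SD, no site | SE with site | Type I error, no site / with site | Power, no site / with site |
|---|---|---|---|---|---|
| 0 | 22.9 | 22.7 | 23.0 | 0.048 / 0.048 | 0.814 / 0.811 |
| 0.05 | 22.8 | 22.6 | 22.4 | 0.053 / 0.054 | 0.803 / 0.811 |
| 0.10 | 22.6 | 21.9 | 21.9 | 0.044 / 0.048 | 0.815 / 0.836 |
| 0.20 | 22.1 | 21.0 | 20.5 | 0.035 / 0.049 | 0.845 / 0.887 |

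Monte Carlo error on the type I rates is about √(0.05 × 0.95/3000) = 0.004, so the conservatism is clear only at ρ = 0.20. Blocking already delivers part of the precision. Power without site at ρ = 0.20 is 0.845, not 0.80, so the realised gain there is about 4 points (0.887 − 0.845).

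**Cox, logistic and Fisher.** Nine equal sites, 500 runs, assumed site SD 1.0 on the log scale.

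- Cox, no treatment effect: without site the reported SE is 0.178 against an actual 0.152, and the rejection rate is 0.026; stratified by site it is 0.046.
- Cox, with an effect: the log hazard ratio is 0.333 without site against 0.435 stratified. The SE is 0.188 against 0.194, slightly larger with site. Power is 0.41 against 0.61. At site SD 0.5, power is 0.60 against 0.66.
- Logistic, with an effect: the estimate is 0.83 without site against 1.02 with it, the SE 0.326 against 0.367, and power 0.74 against 0.80.
- Fisher: rejection rate 0.034 with no effect; power 0.71, against 0.80 for the logistic model with site.

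Monte Carlo error on a 5% rate here is about √(0.05 × 0.95/500) = 0.010. The Fisher null rate was 0.058 at site SD 0.5 and 0.038 with no site effect (600 runs). These runs therefore cannot separate its usual conservatism from that due to omitting site; the power comparison is the more useful one. At site SD 0.5 the logistic null rates were 0.064 without site and 0.076 with site indicators, which argues for a random intercept or a stratified test over nine indicators. The ordinal haze model was not simulated; the logistic result stands in for it.

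**The case against.** The strongest reply is that this is an efficiency preference on secondary outcomes. The direction is conservative, the gain at ρ = 0.05 is about one to two power points, and items 2 and 4 already have planned fits with site. SAP 3.6 expects about three-fourths of patients from one hospital network serving the same population, so large between-site variance cannot be presumed. All of that stands, and it limits the size of the point. It does not supply a site-adjusted version for items 8, 9 and 12. The permutation P-value that respects the blocks is written for the primary test, whereas items 2, 4, 8 and 9 name Wald, likelihood-ratio, Fisher and t-tests.

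Four stronger readings are tempting, and the documents do not support them:

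- **That all five have error bars that are too wide.** This depends on an undocumented between-site variance, and it describes only the linear models. Adding site to the Cox or ordinal model need not narrow the interval, and the Fisher test has no interval.
- **That measurement differences prove site matters.** Protocol 5.4 says "If Heidelberg Spectralis is not available, the Zeiss Cirrus SD-OCT may be used", but nothing shows that any site used the second device, and sites must keep one scanner throughout. Protocol 5.2 has two acuity chart procedures but does not say that chart type follows site. Acuity is a change score, and thickness and haze adjust for baseline, so stable offsets are largely absorbed. The argument is suggestive only.
- **That these five are the only exceptions in an otherwise consistent SAP.** Item 6 also runs an unstratified Fisher test, the pooled adverse-event comparisons (SAP 7.2.2) omit site, and so does the Aim 2 primary model (SAP 3.2.3).
- **That power would rise from 80% to 88% at ρ = 0.20.** The simulation under the SAP's own blocking puts the gain at about 4 points. SAP 3.4.2 also notes that its thickness figure ignores baseline adjustment, which item 9 makes.

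**Conclusion.** The point holds in conditional form. The lead analyses of items 8, 9 and 12 have no committed site-adjusted counterpart; for items 2 and 4 the only question is which version leads. If site is prognostic, all five are conservative. For thickness the excess interval width runs from nil at ρ = 0 to 11.8% at ρ = 0.20, where ρ is the site share of variance left after baseline adjustment. For items 2 and 12 the estimate shrinks toward the null. The Cox and logistic figures rest on assumed site SDs and small simulations, and show direction more reliably than size. A reader might infer that the secondary results would be invalid or prone to false positives. They would not be, and the primary outcome is unaffected. If site is not prognostic, adjusting for it costs next to nothing (thickness half-width 45.3 microns either way). It is a free improvement worth making.

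**What to change.** Amend SAP 3.2.2 so that the site-adjusted version leads:

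- **Item 2:** Cox model stratified by site.
- **Items 4, 9 and 12:** add a site random intercept, keeping the patient random effect in items 4 and 12.
- **Item 8:** Mantel-Haenszel test stratified by site, or logistic regression with a site random intercept, in place of the Fisher test.

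Pool sites with fewer than three observations, as the primary analysis already does, and keep the present models without site as labelled sensitivity analyses. Date the change before the final unmasked analysis, so that the choice of lead version cannot depend on results. The cost is SAP wording and one term or stratum per analysis, with no new data.
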